9.1. Screening Assessments

Prior to screening, all subjects must provide informed consent for study participation, per [Section 13.5](#). The following assessments will be performed according to the time points in the Schedule of Assessments tables ([Table 5](#) and [Table 6](#)).

9.1.1. HIV Testing

Subjects are not required to have a negative serology test for HIV to participate in the study. Testing could be done at the discretion of caregivers.

9.1.2. Confirmation of CAP

Subjects are required to have a confirmed CAP diagnosis at screening. If confirmation is not available, the subject must undergo testing to confirm CAP.

9.1.3. Pregnancy Test

All females of childbearing potential are required to have a negative serum or urine pregnancy test at screening to participate in the study.

9.2. Safety Assessments

The following assessments will be performed according to the time points in the Schedule of Assessments tables ([Table 5](#) and [Table 6](#)).

9.2.1. Demographic/Medical History

A review of demographic parameters, including age, gender, race and ethnicity will be performed at screening.

Past and present medical history will be recorded. Any ongoing condition or signs and symptoms observed prior to the initiation of study treatment should be recorded as medical history.

9.2.2. Vital Signs

Vital signs will include blood pressure, oral temperature, respiration rate, and heart rate, as well as pulse oximetry. Vital signs will be measured during study drug administration at the following time points: predose, at the end of administration, and 30 minutes after the end of administration. Significant findings noticed after the start of study drug that meet the definition of an AE must be recorded in the eCRF.

9.2.3. Physical Examination

All physical examinations, including measurement of body weight, will be performed by a study physician or designee. Height need only be measured at the screening examination. The initial body weight measured at enrollment will be used to calculate rhu-pGSN dosing for all doses (so that an individual subject will always receive the same dose). The physical examination includes skin, head, ears, eyes, nose, throat, heart, lungs, abdomen, and neurologic system. Additional examination may be performed as found relevant by the Investigator.

9.2.4. Outcome Prediction Models

The CURB-65 (Appendix A), PSI (Appendix C), and SOFA (Appendix D) tests will be administered. The cognitive status of the subject will be informally assessed for incorporation in the CURB-65 score by using the mini-mental state examination (MMSE; also referred to as the abbreviated mental test score; Appendix B). If the caregivers are concerned about abnormalities of cognition, subjects will be further evaluated at the discretion of the caregivers, which may involve being asked questions according to the MMSE or similar tool to assess cognitive function.

9.2.5. Electrocardiogram

All EKGs will be conducted and read locally. When EKGs are to be collected at the same time point as a blood collection, EKGs should be collected first. Three serial, resting, supine, 12-lead EKGs will be conducted within 10 minutes total time. The mean of the triplicate EKG measurements performed at screening will serve as the subject's baseline corrected QT (QTc) value for all post-dose comparisons.

EKG parameters to be evaluated include heart rate, the time from the onset of the P wave to the start of the QRS complex (PR), the duration of the entire cardiac cycle, measured in seconds (RR), the combination of three of the graphical deflections (QRS complex), the measure of the time between the start of the Q wave and the end of the T wave (QT) intervals, and the QT interval corrected for heart rate using Fridericia's formula (QTcF).

9.2.6. Laboratory Assessments

All routine clinical laboratory assessments will be performed by the hospital laboratory or equivalent, when appropriate. Where indicated, handling and shipping clinical laboratory samples to a central laboratory will be outlined in the Laboratory Manual.

Screening laboratory and other tests can serve as baseline values for participants (no need to repeat lab tests at entry if done within the prior 36 hours unless dictated by SOC).

The laboratory evaluations will include:

1. Hematology: complete blood count with differential white count and reticulocyte count, and platelet count; PT/PTT
2. Comprehensive metabolic profile (including chemistries/electrolytes, TP/albumin, BUN/creatinine, C-reactive protein (CRP), lactose dehydrogenase (LDH), creatine phosphokinase (CPK), alanine aminotransferase (ALT), aspartate aminotransferase (AST), total bilirubin, alkaline phosphatase, and amylase or lipase)
3. Respiratory function (oxygen saturation by pulse oximetry; arterial blood gas tests only at the caregiver's discretion)

Abnormal laboratory test results considered clinically significant by the Investigator or that require treatment should be reported as AEs in the eCRF.

9.3. Pharmacokinetic Assessments

For the one dose in the SD arm and the first 2 doses in the MAD arms, blood will be drawn within 30 minutes predose, and 5-10 minutes after the end of administration, as well as 2, 8, 12 and/or 16, and 24 hours after the end of administration (\pm 30 minutes) for analysis of plasma for C_{max} , T_{max} , $T_{1/2}$, AUC_{0-8} , AUC_{inf} . Sampling at both the 12- and 16-hour time points is encouraged where feasible, but only one of these two times is required. Identical PK sampling is encouraged on Day 3 where feasible but not required in the multiple-dose arms.

9.4. Pharmacodynamic Assessments

A 10-mL aliquot (equal parts serum and plasma spun from 20 mL of whole blood) collected on study days indicated in [Table 5](#) and [Table 6](#) will be frozen for subsequent analysis of the following:

- Biomarkers including, but not limited to, procalcitonin, pGSN, $TNF\alpha$, $TGF\beta$, $IL1\beta$, $IL1ra$, $IL2$, $IL4$, $IL6$, $IL10$, $IL17a$ levels

9.5. Other Assessments

Other analyses to be performed include:

- Blood, sputum, and other cultures as clinically indicated (note that a sputum culture is mandatory if a sputum specimen can be obtained and blood cultures are strongly encouraged at entry into the study)
- Sputum neutrophil elastase (where feasible at entry and near the conclusion of study therapy)

10. ADVERSE EVENT MANAGEMENT

10.1. Definition of Adverse Events

10.1.1. Adverse Event (AE)

An AE is the development of an undesirable medical condition or the worsening of a pre-existing medical condition following or during exposure to a pharmaceutical product, whether or not considered causally related to the product.

10.1.2. Serious Adverse Event (SAE)

A serious adverse event (SAE) is an AE occurring during any study phase (i.e., baseline, treatment, or follow-up), and at any dose of the investigational product, comparator or placebo, that fulfils one or more of the following:

- Results in death
- It is immediately life-threatening
- It requires in-patient hospitalization or prolongation of existing hospitalization
- It results in persistent or significant disability or incapacity
- Results in a congenital abnormality or birth defect
- It is an important medical event that may jeopardize the subject or may require medical intervention to prevent one of the outcomes listed above.

All SAEs that occur after a subject has signed the consent form and has been randomized, including before or during treatment and within 28 days following the cessation of treatment, whether or not judged to be related to the study, must be recorded on forms provided by the Sponsor.

10.2. Clarifications to Serious Adverse Event Reporting

Death is an outcome of an SAE and not an SAE in itself. When death is an outcome, report the event(s) resulting in death as the SAE term (e.g., “pulmonary embolism”). If the cause of death is unknown, report “Death, unknown cause” as the SAE term.

10.3. Assessment of Causality

The relationship of each AE to the study drug administration will be assessed by the Investigator after careful consideration of all relevant factors such as (but not limited to) the underlying study indication, coexisting disease, concomitant medication, relevant history, pattern of the AE, temporal relationship to receipt of the study medication and de-challenge or re-challenge according to the following guidelines:

YES (possible, probably or definitely related): there is a reasonable possibility that the study drug caused the event; one or more of the following criteria apply:

- The event follows a reasonable temporal sequence from administration of study drug.

- The event could not be reasonably attributed to the known characteristics of the subject's clinical state, environment or toxic factors or other modes of therapy administered to the subject.
- The event follows a known pattern of response to study drug.
- The event disappears or decreases on cessation or reduction in dose of the study drug. In some situations, an AE will not disappear or decrease in intensity upon discontinuation of the study drug despite other clear indications of relatedness.

NO (probably not related or definitely not related): There is no reasonable possibility that the study drug caused the event; one or more of the following criteria apply:

- The event does not follow a reasonable temporal sequence from administration of study drug.
- The event could be reasonably attributed to the known characteristics of the subject's clinical state, concurrent illness, environment or toxic factor or other modes of therapy administered to the subject.
- The event does not follow a known pattern of response to study drug.
- The event does not disappear or decrease on cessation or reduction in dose of the study drug, and it does not reappear or worsen when the study drug is re-administered.

10.4. Assessment of Severity

The severity rating of an AE refers to its intensity. The severity of each AE will be categorized using the NCI CTCAE, v 4.03 (or higher). For any term that is not specifically listed in the CTCAE scale, intensity should be assigned a grade of 1 through 5 using the following CTCAE guidelines:

- Grade 1: Mild; asymptomatic or mild symptoms; clinical or diagnostic observations only; intervention not indicated
- Grade 2: Moderate; minimal, local or noninvasive intervention indicated; limiting age-appropriate instrumental activities of daily living
- Grade 3: Severe or medically significant but not immediately life-threatening; hospitalization or prolongation of hospitalization indicated; disabling; limiting self-care activities of daily living
- Grade 4: Life-threatening consequences; urgent intervention indicated
- Grade 5: Death related to AE

It is important to distinguish between serious and severe AEs. Severity is a measure of intensity whereas seriousness is defined by the criteria under [Section 10.1.2](#). An AE of severe intensity may not be considered serious.

10.5. Pregnancy or Drug Exposure during Pregnancy

If a subject becomes pregnant during the study, administration of study drug is to be discontinued immediately.

Pregnancies must be reported within 24 hours of the Investigator's knowledge using the Sponsor's pregnancy form.

Pregnancy in itself is not regarded as an AE or SAE unless there is a suspicion that an investigational product may have interfered with the effectiveness of a contraceptive medication.

The outcome of all pregnancies (spontaneous miscarriage, elective termination, normal birth or congenital abnormality) must be followed up and documented even if the subject was discontinued from the study.

All reports of congenital abnormalities/birth defects are SAEs. Spontaneous miscarriages should also be reported and handled as SAEs. Elective abortions without complications should not be handled as AEs.

10.6. Laboratory Abnormalities

To the extent possible, all laboratory abnormalities observed during the course of the study will be included under a reported AE term describing a clinical syndrome (e.g., elevated BUN and creatinine in the setting of an AE of "renal failure"). In these cases (e.g., an AE of renal failure), the laboratory abnormality itself (e.g., elevated creatinine) does not need to be recorded as an AE.

If a laboratory abnormality cannot be reported as a clinical syndrome, AND if the laboratory abnormality results in a therapeutic intervention (i.e., concomitant medication or therapy), is a DLT, or is judged by the Investigator to be of other clinical relevance, then the laboratory abnormality should be reported as an AE.

Subjects experiencing AEs or clinically significant laboratory abnormalities will be assessed and appropriate evaluations performed until all parameters have returned to baseline levels or are consistent with the subject's then-current physical condition.

10.7. Reporting Adverse Events

All AEs, serious and nonserious, will be fully documented on the appropriate eCRF. For each AE, the Investigator must provide its duration (start and end dates or ongoing), intensity, assessment of causality and whether specific action or therapy was required.

All AEs that occur from the signing of the informed consent form (ICF) until the first dose of study drug should be recorded on the AE eCRF page only if the event was related to a study procedure. All other AEs/findings prior to first dose of study drug should be recorded as medical history on the applicable eCRF page. All AEs occurring from the first dose of study drug until 28 days after the last dose of study drug must be recorded on the AE eCRF.

All SAEs (related and unrelated) must be reported to the Sponsor within 24 hours of the Investigator's knowledge. This should be done by faxing/emailing the completed SAE Report Form to the number provided on the SAE Report Form. After the EOS Visit, only new treatment-related SAEs need to be captured on the AE eCRF and reported to the Sponsor.

Investigators must follow subjects with AEs/SAEs until the event has resolved, the condition has stabilized, withdrawal of consent, the subject is lost to follow up or death OR until the EOS Visit, whichever occurs first. New and ongoing treatment-related SAEs should be followed beyond the EOS Visit. If the subject dies, this should be captured as the outcome of the AE unless no link between the AE and the subject death can be established, in which case the AE will be marked as ongoing and the death will be reported as a separate event.

If a subject is lost to follow up, this should be captured accordingly within the AE eCRF and on the follow up SAE report.

The Sponsor or designee is responsible for notifying the relevant regulatory authorities of applicable suspected unexpected serious adverse reactions (SUSARs) as individual notifications or through periodic line listings. It is the Principal Investigator's responsibility to notify the Institutional Review Board (IRB) or IEC of all SAEs that occur at his or her site. Investigators will also be notified of all unexpected, serious, drug-related events (7/15 Day Safety Reports) that occur during the clinical trial. Each site is responsible for notifying its IRB or IEC of these additional SAEs.

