5.2.2. Secondary Endpoints

- PK for rhu-pGSN including, but not limited to maximum concentration (C_{max}), time to maximum concentration (T_{max}), terminal half-life ($T_{1/2}$), area under the curve from time zero to 8 hours (AUC_{0-8}), area under the curve from time zero to infinity (AUC_{inf}) (levels measured within 30 minutes predose, 5-10 minutes after the end of administration, and 2, 8, 12 and/or 16, and 24 hours (\pm 30 minutes) after each dose (Day 3 sampling in multiple-dose arms is optional)

- Incidence, causality, and severity of AEs and SAEs graded according to the NCI CTCAE version 4.03 (or equivalent); clinically significant laboratory and/or EKG abnormalities as required by SOC; death irrespective of cause; cause of death per investigator, including relationship to study drug; use of vasopressors, intubation, or transfer to the ICU or equivalent through Day 28 (secondary time point)

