6.7. Total Duration of Subject Participation

Subjects will be observed for 28-days post-first dose.

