11.4.3. Pharmacokinetics and Immunogenicity

To complete the PK analyses, plasma specimens will be periodically sampled relative to study drug administration and stored frozen for pGSN measurements. For the 1 dose in the SD arm and the first 2 doses in the MAD arms, blood will be drawn within 30 minutes predose, and 5-10 minutes after the end of administration, as well as 2, 8, 12 and/or 16, and 24 hours after the end of administration (± 30 minutes) for analysis of C_{max} , $T_{1/2}$, AUC_{0-8h} , and AUC_{inf} . Identical PK sampling is encouraged on Day 3 where feasible (but not required) in the multiple-dose arms.

Immunogenicity will be assessed at the last visit on Day 28 ± 2 days. Antibodies against rhu-pGSN will be assayed from frozen specimens to determine whether the investigational product induces an antibody response in recipients.

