#### 11.1.2 Biostatistical methods

All AEs will be coded using MedDRA.

All AE summaries will be restricted to TEAEs only. Summary tables will include the number of subjects (%) experiencing an event and the number of events. Subjects will be counted only once at each system organ class (SOC) and preferred term (PT) level of summary.

The TEAE summaries will include:

- TEAE summary by SOC and PT
- TEAE summary of serious events by SOC and PT
- TEAE summary of deaths by SOC and PT
- TEAE summary by severity (NCI-CTCAE) by SOC and PT
- TEAE summary by causality to Study Drug by SOC and PT
- TEAE summary by causality to Study Procedure by SOC and PT
- TEAE summary of events leading to treatment discontinuation (Drug withdrawn) by SOC and PT

All AEs will be listed and will include verbatim term, PT, SOC, treatment, severity, causality, seriousness, and action taken with regards to the study drug. Separate listings will be created for SAEs, deaths and events leading to treatment discontinuation (Drug withdrawn).

Overall survival (time to death in days) will be analyzed through Kaplan-Meier methods and censored at the time of the study exit visit. Date of death will be taken as the SAE end date for which the outcome is stated to be fatal. Overall survival (days) = Date of event outcome of death/ Date of study exit - Date of first study drug administration + 1.

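### Section 10.7 conflicts with itself and with 10.1.2 on when unrelated events stop being recorded, so safety data through Day 28 and the 28-days-after-last-dose window may be cut short

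*Protocol*

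**What the plan says.** **Rules that require full capture.** Protocol 10.7 says that all AEs from the first dose "until 28 days after the last dose of study drug must be recorded on the AE eCRF". Protocol 10.1.2 requires all SAEs to be recorded "within 28 days following the cessation of treatment, whether or not judged to be related to the study".

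**Rules that allow less.** The same section 10.7 says: "After the EOS Visit, only new treatment-related SAEs need to be captured on the AE eCRF and reported to the Sponsor". It also limits follow-up of AEs and SAEs to resolution, stabilization, withdrawal of consent, or when "the subject is lost to follow up or death OR until the EOS Visit, whichever occurs first". Only treatment-related SAEs are followed beyond that visit.

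**Timing of the visit.** Tables 5 and 6 place the EOS visit at Day 28 with a window of 4 days either side. Protocol 11.4.3 gives a different tolerance: "Immunogenicity will be assessed at the last visit on Day 28 ± 2 days". The synopsis repeats it.

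**What depends on it.** The secondary safety endpoint (Protocol 5.2.2) covers AEs, SAEs, deaths from any cause, vasopressors, intubation and ICU transfer "through Day 28 (secondary time point)". Survival to 28 days is an exploratory outcome (5.2.3). Protocol 6.7 states: "Subjects will be observed for 28-days post-first dose".

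**The SAP.** Section 11.1.2 has overall survival "censored at the time of the study exit visit" and takes the date of death from the end date of a fatal SAE. Section 3 applies no visit windows.

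**The concern.** The full-capture rules and the post-EOS sentence agree only if the EOS visit falls on or after the end of the last-dose window. The schedule allows it earlier. For the days in between, one sentence tells the site to record every event and another tells it that only treatment-related SAEs are needed.

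This matters because the secondary endpoint counts deaths irrespective of cause. If a site relies on the post-EOS sentence, whether a late death, ICU transfer or readmission enters the database depends on the investigator's opinion about cause. A related death on Day 26 would be recorded and an unrelated one might not be.

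The SAP does not repair this. Deaths come from SAE records, so an uncaptured fatal SAE leaves no death in the data, and the survival summary would list the subject among those who did not die. AE summaries are counts and percentages of subjects, so unobserved days count as event-free. The one later safety contact in the protocol (6.9) is for a subject who withdraws and refuses further assessment. Nothing equivalent exists for a completer seen early.

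**Working it through.** The plan states no figure to reproduce. The check is day arithmetic.

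**Inputs**
- Day 1 is the first day of study treatment (footnotes to Tables 5 and 6).
- Last dose: Day 1 in SD, Day 3 in MAD (Protocol 6.3).
- EOS visit: Day 24 to 32 (Tables 5 and 6), or Day 26 to 30 (synopsis and 11.4.3).

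**Formulas**
- End of recording window = last-dose day + 28. SD: 1 + 28 = Day 29. MAD: 3 + 28 = Day 31.
- Shortfall = max(0, end of window − EOS day).

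| EOS visit | Days short of Day 28 | Days short, SD (Day 29) | Days short, MAD (Day 31) |
|---|---|---|---|
| Day 24 (earliest under ±4) | 4 | 5 | 7 |
| Day 26 (earliest under ±2) | 2 | 3 | 5 |
| Day 28 (on time) | 0 | 1 | 3 |
| Day 30 | 0 | 0 | 1 |
| Day 31 or 32 | 0 | 0 | 0 |

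At the extreme, 4 of 28 days (14%) are open for the Day 28 endpoint. In MAD, 21 of the 28 days after the last dose are covered. With the EOS visit as the cut-off, only a visit on Day 29 or later (SD) or Day 31 or later (MAD) satisfies 10.7 and 10.1.2. By the SAP formula (exit − first dose + 1), a subject leaving on Day 24 is censored at 24 days.

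**Illustration of events at risk.** The documents give no late event rate, so this rests on assumptions: a constant hazard over 28 days, and a 28-day event probability p of 5%, 10% or 20%. With h = −ln(1 − p)/28, the probability of an event after Day 24 and by Day 28 is p − [1 − exp(−24h)]. For p = 10%, h = 0.1054/28 = 0.00376, and the difference is 0.1000 − 0.0864 = 0.0136.

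| p | Event in Days 25–28 | Expected in 32 subjects, all seen on Day 24 | Chance of at least one |
|---|---|---|---|
| 5% | 0.0070 | 0.22 | 20% |
| 10% | 0.0136 | 0.44 | 36% |
| 20% | 0.0259 | 0.83 | 57% |

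These are upper figures, with every subject seen on the earliest day and every such event left unrecorded. If visits were instead spread evenly over Days 24 to 32, the mean shortfall against Day 28 would be (4 + 3 + 2 + 1)/9 = 1.1 days, and the expected counts fall to about 0.06, 0.12 and 0.23. Events concentrated early in the illness would lower them further.

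**A further ambiguity.** Protocol 6.2 and the synopsis define Day 1 for analysis as the day of admission. If a site counts visits from admission and the first dose falls on the next calendar day, each shortfall measured from dosing grows by one day.

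**The case against.** The strongest reply is that capture does not simply end at the EOS visit. Two mandatory rules already require the events in question, and the post-EOS sentence sets a minimum without forbidding anything. A site that left out an unrelated death on Day 26 would breach both 10.1.2 and the other sentence in 10.7. This stands. A reader might infer that an early visit necessarily loses unrelated events. The documents support only that they may be missed by a site that follows the permissive sentence.

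Second, Day 24 is the extreme. Under ±2 days the Day 28 shortfall is at most 2 days. This also stands, and both figures are given above. A reader might go on to infer that a large share of subjects would be censored before Day 28. The documents give no distribution of visit dates, and such a count would treat a subject one day short like one four days short.

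Third, the consequences are limited. The primary endpoint and the escalation reviews use Day 7, all analyses are descriptive, and Kaplan-Meier censoring allows for unequal follow-up. The first two points stand. The third stands only in part. Censoring handles different exit dates, but it does not help the simple counts of deaths and AEs. It also does not correct a record in which related deaths after the visit are captured and unrelated ones may not be.

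**Conclusion.** The point holds as an internal inconsistency that permits incomplete capture. It does not show that events will be lost. For a site following the post-EOS sentence, unrelated AEs, SAEs or deaths may go unrecorded for up to 4 days before Day 28 (2 under ±2). Against the last-dose window the gap is up to 7 days in MAD and 5 in SD (5 and 3 under ±2). In MAD the conflict arises even for a visit on Day 28, which is 3 days short, so it does not depend on early scheduling.

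The affected outcomes are the secondary safety endpoint through Day 28 and exploratory 28-day survival. The day counts assume that Day 1 is the first dose. The expected number of missed events is probably below one, on assumed event rates. It is still worth correcting, because an all-cause endpoint should not depend on a causality judgement, and events that were never collected cannot be recovered at analysis.

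**What to change.** 1. **Protocol 10.7.** Replace the post-EOS sentence with wording such as: All AEs, SAEs and deaths, regardless of relatedness, are recorded to 28 days after the last dose (Day 29 in SD, Day 31 in MAD). After that date, only new treatment-related SAEs need be recorded. Apply the same date to the follow-up limit that now ends at the EOS visit. This brings 10.7 into line with 10.1.2.
2. **Telephone contact.** For any subject, SD or MAD, whose EOS visit precedes that date, add one telephone safety and vital-status contact on or after it.
3. **SAP 11.1.2.** Censor survival at the last confirmed vital-status date in place of the exit visit.
4. **Visit window.** Reconcile the ±4 days in Tables 5 and 6 with the ±2 days in 11.4.3 and the synopsis, and state one definition of Day 1.

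The EOS window need not be made one-sided. The telephone contact closes the gap, and a one-sided window would shift the Day 28 antibody sample later for no further gain.

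The cost is protocol and SAP wording plus one short call for subjects seen before their window ends, including an SD subject seen on Day 28. No visits, samples or subjects are added.
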